5. **Blood/serum sample collection for clinical safety laboratory assessment.** The Day 3 and 7 sampling will occur before the 1st dose of study drug.
6. **Urine sample collection drug screening:** cannabinoids, cocaine, amphetamines, opiates, methamphetamines.
7. **Overnight sputum collection for eligibility assessment.** Sputum assessment, including volume, will be performed by a Sponsor-approved central laboratory (see laboratory study instruction document). The 1st of the 3 overnight sputum collections (Day -7 to Day -3) conducted during the Screening Period will be used to assess eligibility as follows: sputum volume (must be at least 10 mL), acid-fast bacilli detection, *Mycobacterium tuberculosis* (Mtb) positivity and rifampicin sensitivity via the GeneXpert® diagnostic system (Cepheid). In case inclusion criteria cannot be met from the 1st overnight sputum collection, one or more of the above procedures can be conducted on a 2nd overnight sputum collected during the Day -7 to -3 screening period if the patient is domiciled at the site for both.
8. **Vital sign and body weight recording.** The following 5 vital signs will be recorded: axillary body temperature (BT), respiratory rate (RR), heart rate (HR), systolic blood pressure, (SBP), diastolic blood pressure (DBP). Body weight (BW) will also be recorded with vital signs. Vital signs and body weight will be recorded as follows:
 - Screening Phase: vital signs and BW once in the morning at approximately the same time the 1st daily dose study drug will be administered. SBP, DBP and HR can be repeated twice if exclusion criteria are met.
 - Study Treatment Phase: vital signs and BW once every morning (Days 1 to 14) before administration of the 1st daily dose of study drug; in addition, on Days 1, 4, 7, 10 and 14 vital signs will also be collected 2.5h, 10.5h and 16.5h after the time of 1st daily dose of study drug (see Table 4).
 - Follow-up Phase: vital signs and BW on Day 15 in the morning before 1st daily dose of SoC medication; on Days 28 and 42 during the visit.

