 - EWV: vital signs and BW if the participant withdraws from the study between Day 1 and 14.At each time point BT, RR and BW will be measured once, whereas HR, SBP and DBP will be measured twice as follows: after 10 min supine (“manual, supine”) and after 2 (± 0.5) min standing (“manual, 2-min standing”). When ECG, vital signs and/or blood/serum samples are to be obtained at the same time point, the following order must be followed: ECG, vital signs, blood/serum sample, within 5 min of each other.
9. **ECG recording.** 12-lead ECG will be recorded once at each time point after at least 10 minutes of supine rest as follows:
 - Screening Phase: once in the morning at approximately the same time the 1st daily dose study drug will be administered.
 - Study Treatment Phase: on Days 1, 4, 7, 10 and 14 before administration of the 1st daily dose of study drug and 2.5h, 10.5h and 16.5h thereafter (see Table 4).
 - Follow-up Phase: on Day 15 in the morning before 1st daily dose of standard of care medication; on Days 28 and 42 during the visit.
 - EWV: if the participant withdraws from the study between Day 1 and 14.
10. **Eye assessment.** A trained staff member will assess: i) eye symptoms using a standardized script (Section 10.5, Appendix 5), ii) visual acuity by means of the Rosenbaum Pocket Eye Screener, iii) color vision by means of the Waggoner Computerized Color Vision Test and as follows:
 - Screening Phase: once in the AM.
 - Study Treatment Phase: Days 1, 4, 7, 10, and 14, 2.5h after 1st daily dose of study drug (see Table 4).
 - Follow-up Phase: Days 15, 28 and 42 during the visit.
 - EWV: if the participant withdraws from the study between Days 1 and 14.

11. **Study drug (IMP) administration.** Study drug (TBA-7371 or HRZE) will be administered from Day 1 to Day 14 based on the randomization list by an authorized and trained site staff member. The 1st dose of study drug will be administered at the same time each Day for the individual participant. Subsequent doses will be administered as follows (see Table 4):
 - Twice daily (BID) schedules: 12h after 1st dose
 - Three times (TID) daily schedule: 7h and 14h after 1st doseFasting must occur at least 2 hours before dosing and at least 1 hour after dosing. Study drug administration will be followed by 200 mL water.

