9.4.2.2. Secondary Safety Analyses

Individual safety parameters of interest, e.g., mean HR over time, mean SBP and DBP over time, and incidence of and frequency of eye symptoms and other adverse events will be summarized by treatment group. The incidence of AEs by seriousness, severity, body system, preferred term and relatedness to study drug will be summarized by treatment group.

Mean and frequency distribution of changes from baseline through Day 15 in HR, SBP and DBP will be provided by treatment group and by each method measured. The frequency of participants with $\geq 25\%$ increase in HR, decrease in SBP, decrease in DBP vs. baseline as measured with any of the methods will be provided by treatment group. The mean and frequency distribution of percentage of days with $\geq 25\%$ increase in HR, decrease in SBP, decrease in DBP vs. baseline will be provided by treatment group. The mean and median RR, QRS, QT, QTcF values from ECG will be provided by treatment group.

The mean change in HR, SBP and DBP from Day 1 to Days 4, 7, 10, 14 and 15 will be provided by treatment group and by each method measured. The change in frequency of participants with eye symptoms (all, severe, serious) and abnormal visual acuity and abnormal color vision scores from Day 1 to Days 4, 7, 10, 14 and 15 will be provided by treatment group. The mean change in HR, SBP and DBP from screening to Days 28 and 42, and from Day 14 to Days 28 and 42 will be provided by treatment group and by each method measured. The change in frequency and duration of eye symptoms (all, severe, serious) and/or abnormal visual acuity and/or abnormal color vision scores from screening to Days 28 and 42, and from Days 1-14 (combined) to Days 28-42 (combined) will be provided by treatment group.

The mean, median and range of each blood/serum and urine safety parameter at screening, Day 3, Day 7, Day 14 and Day 42 will be provided by treatment group. The mean, median and range of the changes in each blood/serum and urine safety parameter from screening to Day 3, Day 7, Day 14 and Day 42 will be provided by treatment group. Changes may be assessed on the raw (difference) or log (fold change) scale, depending on the whether the distribution of the measure is more appropriately described by a normal or lognormal distribution, respectively.

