12.5.2 Daily Vital Signs Results

Daily values of vital signs (HR, SBP, and DBP) measured while in supine and while in standing at baseline (Day 1 predose), Days 2 (predose), 3, 4 (predose), 5, 6, 7 (predose), 8, 9, 10 (predose), 11, 12, 13, 14 (predose), 15, 28, and 42 and changes from baseline will be summarized by treatment group using descriptive statistics. Line plots of mean of daily HR, SBP, and DBP measured while in supine and while in standing by treatment group will be provided.

Potentially clinically important criteria for changes from baseline in HR, SBP, and DBP while measured in supine and while in standing are defined as follows:

- $\geq 25\%$ increase in supine HR

- $\geq 25\%$ increase in standing HR
- $\geq 25\%$ decrease in supine SBP
- $\geq 25\%$ decrease in standing SBP
- $\geq 25\%$ decrease in supine DBP
- $\geq 25\%$ decrease in standing DBP

For each of the criteria, the frequency and proportion (expressed in percent) of participants who met the criterion at each time point will be provided by treatment group. For the by-time point summary, the denominator for the proportion is the number of participants in the treatment group with non-missing values at baseline and the given post-baseline time point.

For each of the criteria, any day that a participant whose vital signs results met the criterion will be counted toward the number of days with the criterion met in the study for that individual. Number of days with the criterion met will be summarized by treatment group using descriptive statistics.

Additionally, categorical number of days with the criterion met will be summarized by treatment group as follows:

- 1-3 days
- 4-6 days
- 7-9 days
- 10-12 days
- 13-15 days
- ≥ 16 days

The summary will include the frequency and proportion (expressed in percent) of participants for each category. For computing proportions, the denominator will be the number of participants in the treatment group who met the respective criterion.

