12.5.3 Orthostatic Vital Signs Results

Orthostatic change in HR, SBP, and DBP is calculated as vital signs measurement recorded in standing position minus vital signs measurement recorded in supine position at same time point. Percentage orthostatic change in HR, SBP, and DBP is calculated as vital signs measurement recorded in standing position minus vital signs measurement recorded in supine position at same time point divided by vital signs measurement recorded in supine position at same time point.

Orthostatic changes in HR, SBP, and DBP at predose, and 2.5h, 10.5h, and 16.5h after the time of 1st daily dose of study drug on Days 1, 4, 7, 10, and 14 and daily measurements at Baseline, Days 2, 3, 4, 5, 6, 7, 8, 9, 10, 11, 12, 13, 14, 15, 28, and 42 will be summarized by treatment group using descriptive statistics. Line plots of mean of orthostatic change in HR, SBP, and DBP measured while in supine and while in standing by treatment group will be provided.

Potentially clinically important criteria for orthostatic hypotension are defined as follows:

- $\geq 25\%$ increase in orthostatic HR

- $\geq 25\%$ decrease in orthostatic SBP
- $\geq 25\%$ decrease in orthostatic DBP
- ≥ 20 mmHg decrease in orthostatic SBP
- ≥ 10 mmHg decrease in orthostatic DBP

For each of the criteria, the frequency and proportion (expressed in percent) of participants who met the criterion at each time point will be provided by treatment group. For the by-time point summary, the denominator for the proportion is the number of participants in the treatment group with non-missing values at the given time point.

Any day that a participant met a potentially clinically important criterion of orthostatic hypotension will be counted toward the number of days with orthostatic hypotension in the study for that individual. Number of days with orthostatic hypotension will be summarized by treatment group using descriptive statistics for each of the criteria.

Additionally, categorical number of days with orthostatic hypotension will be summarized by treatment group as follows:

- 1-3 days
- 4-6 days
- 7-9 days
- 10-12 days
- 13-15 days
- ≥ 16 days

The summary will include the frequency and proportion (expressed in percent) of participants for each category. For computing proportions, the denominator will be the number of participants in the treatment group who met the respective criterion.

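### Day counts for heart rate and blood pressure changes leave out post-dose readings in SAP 12.5.2 and depend partly on the reading schedule in SAP 12.5.3, and the stated percentage of days is not reported

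*SAP*

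**What the plan says.** **Schedule.** Footnote 8 of the Schedule of Activities (Protocol 1.3) sets "vital signs and BW once every morning (Days 1 to 14) before administration of the 1st daily dose of study drug", and adds that "on Days 1, 4, 7, 10 and 14 vital signs will also be collected 2.5h, 10.5h and 16.5h after" the first daily dose. ECG heart rate, the third heart rate method, has post-dose recordings on the same five days: "on Days 1, 4, 7, 10 and 14 before administration of the 1st daily dose of study drug and 2.5h, 10.5h and 16.5h thereafter".

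**Days with a 25% or greater change.** SAP 12.5.2 takes Day 1 pre-dose as baseline and lists the daily values as "Days 2 (predose), 3, 4 (predose), 5, 6, 7 (predose), 8, 9, 10 (predose), 11, 12, 13, 14 (predose), 15, 28, and 42". The days in that list without a pre-dose label (3, 5, 6, 8, 9 and 11–13) have only a pre-dose reading under the protocol schedule. The section then states that "any day that a participant whose vital signs results met the criterion will be counted toward the number of days with the criterion met". This count runs over the whole study.

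**Days with orthostatic hypotension.** SAP 12.5.3 lists the pre-dose, 2.5h, 10.5h and 16.5h readings of the five days together with the daily measurements. It then applies the same rule: "Any day that a participant met a potentially clinically important criterion of orthostatic hypotension will be counted toward the number of days".

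**Reporting.** Both sections group the number of days from 1–3 up to 16 or more. The denominator is the participants who met the criterion. Protocol 9.4.2.2 promises something else for the 25% criteria: "The mean and frequency distribution of percentage of days with" such a change against baseline. The endpoint tables (Protocol 3.2, SAP 6.4) give the window as Day 1 through Day 15. SAP section 8 reports no changes from the protocol.

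**The concern.** A percentage-of-days endpoint should show how much of the treatment period a participant spends with a meaningful heart rate rise or blood pressure fall. Protocol 2.3 names these among the most common phase 1 events and describes most events as transient. An effect that follows each dose and fades overnight is therefore the case the endpoint most needs to detect, and a trough reading is least able to show it.

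The two sections fall short in different ways. In 12.5.2 every dosing day is read alike, but only at trough. In 12.5.3 a day has four chances to count or one, depending on where it falls in the schedule.

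The trough reading is also not equally far from the last dose in every regimen. Protocol 4.3 says that fractionated and once-daily dosing are to be compared on safety and tolerability, so an omission that can differ by regimen bears on that comparison.

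**Working it through.** The plan gives no figure for this point, so there is none to reproduce.

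**1. Coverage.** Post-dose readings fall on 5 of 14 dosing days: 5/14 = 36%. The other nine dosing days have one pre-dose reading per position.

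**2. Time from last dose to the next pre-dose reading.** From the dose times in Protocol 1.3:
- QD: 24h
- BID: 24 − 12 = 12h
- TID: 24 − 14 = 10h

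**3. Days that can count.** In 12.5.2, Days 2–15 plus 28 and 42 give 14 + 2 = 16. If every reading counted, Day 1 would be added, giving 17. Days 1–15 supply at most 15, so the category of 16 or more days cannot be reached without Day 28 or Day 42, when study drug has stopped.

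**4. Share of affected dosing days captured.** The documents give no rates, so these are assumptions. Let p be the chance that a dosing day has a post-dose reading meeting the criterion, and q the chance that its pre-dose reading does, independently. For the 25% criteria q = 0 on Day 1, because that reading is the baseline.
- True days: T = p + 13 × [1 − (1 − p)(1 − q)]
- All readings count: A = p + 4 × [1 − (1 − p)(1 − q)] + 9q
- Pre-dose values only: B = 13q

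Example, p = 0.5 and q = 0.2: T = 0.5 + 13 × 0.6 = 8.3. A = 0.5 + 2.4 + 1.8 = 4.7. B = 2.6.

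| p | q | T | A (A/T) | B (B/T) |
|---|---|---|---|---|
| 1 | 0 | 14.00 | 5.00 (36%) | 0 (0%) |
| 0.5 | 0 | 7.00 | 2.50 (36%) | 0 (0%) |
| 1 | 0.05 | 14.00 | 5.45 (39%) | 0.65 (5%) |
| 0.5 | 0.2 | 8.30 | 4.70 (57%) | 2.60 (31%) |
| 0.3 | 0.5 | 8.75 | 7.40 (85%) | 6.50 (74%) |

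With q = 0, A/T is 5/14 = 36% at any p. Over p from 0.3 to 1 and q from 0.05 to 0.5, A/T runs from 39% to 85% and B/T from 5% to 74%.

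**5. Orthostatic count.** Standing is compared with supine at the same time point, so Day 1 pre-dose can count. T = 14 × [1 − (1 − p)(1 − q)] and A = 5 × [1 − (1 − p)(1 − q)] + 9q. For p = 0.5, q = 0: 2.5 of 7 days (36%). For p = 0.5, q = 0.2: 4.8 of 8.4 days (57%).

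**6. One participant.** Suppose the effect follows every dose and is gone by morning, so 14 days are affected. For the 25% criteria, 12.5.2 as plainly read scores 0, and the participant is missing from the category table because its denominator holds only those who met the criterion. For an orthostatic effect, 12.5.3 scores 5, which falls in the 4–6 day category rather than 13–15.

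**The case against.** The strongest defence is that 12.5.2 is headed as the daily section and 12.5.1 as the intraday one. On that division 12.5.2 is a consistent trough count with one comparable reading per dosing day. This stands. A reader might infer that the 25% count is itself driven by uneven sampling, but the listed values do not support that. Uneven sampling is explicit only in 12.5.3.

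A reader might also infer that the plan scores an unobserved post-dose period as a day free of the effect within a percentage. The SAP has no denominator of days, so that goes too far. The actual discrepancy is that a number of days replaces the stated percentage.

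A third tempting step is to quote one large understatement. Protocol 2.3 says only of vision-related events that they cleared before the following dose. For heart rate and blood pressure it reports mostly mild, transient events and apparent tachyphylaxis. Nothing fixes the pre-dose rate, and orthostatic criteria can be met pre-dose without any drug effect. Only a range is defensible.

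Post-dose data do appear elsewhere. SAP 12.5.1 and 12.5.3 give proportions by time point with observed denominators, and relevant adverse events of special interest are tabulated. These limit the harm but do not fill the gap: 12.5.1 does not count days, and it compares with the same day's pre-dose value, which is the Day 1 baseline only on Day 1. The schedule is common to all arms, but the time from last dose to trough is not, so a common schedule does not guarantee an equal omission.

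**Conclusion.** The point holds in a limited form. The 5-of-14 coverage and the pre-dose list in 12.5.2 follow directly from the documents, as does the pooling of readings in 12.5.3. So does the mismatch between a number of days that can include Days 28 and 42 and a percentage over Days 1–15. That percentage is stated for changes against baseline, so the mismatch with the endpoint is in 12.5.2; 12.5.3 repeats the construction.

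The size depends on how much of the effect persists to the next morning, which the documents do not give. The 36% and 0% figures are the limit of complete overnight clearance; the wider ranges rest on assumed, independent rates that stay constant over the dosing days. The omission can differ between QD, BID and TID, but the documents do not show that it does or by how much. The harm is confined to descriptive secondary safety summaries; the by-time-point tables are unaffected, and no test or decision rule uses the counts.

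**What to change.** In SAP 12.5.2 and 12.5.3, state which readings enter each day count, and report two summaries:

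- (a) The share of observed days among Days 1, 4, 7, 10 and 14 on which any scheduled reading meets the criterion. Use the Day 1 pre-dose baseline for 12.5.2, and standing versus supine at the same time point for 12.5.3.
- (b) A separately labelled pre-dose (trough) share over Days 2–15.

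Use each participant's observed days as denominator, include participants with zero days, limit the window to Days 1–15, and replace the categories from 1–3 to 16 or more days with ones that fit. Summary (a) should stand beside (b). Replacing the Day 1–15 percentage-of-days endpoint with the five-day share alone would itself depart from the protocol.

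The cost is SAP wording and programming on data already scheduled for collection. The downside is that the post-dose summary rests on at most five days per participant.

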12.5.3 Orthostatic Vital Signs Results

Orthostatic change in HR, SBP, and DBP is calculated as vital signs measurement recorded in standing position minus vital signs measurement recorded in supine position at same time point. Percentage orthostatic change in HR, SBP, and DBP is calculated as vital signs measurement recorded in standing position minus vital signs measurement recorded in supine position at same time point divided by vital signs measurement recorded in supine position at same time point.

Orthostatic changes in HR, SBP, and DBP at predose, and 2.5h, 10.5h, and 16.5h after the time of 1st daily dose of study drug on Days 1, 4, 7, 10, and 14 and daily measurements at Baseline, Days 2, 3, 4, 5, 6, 7, 8, 9, 10, 11, 12, 13, 14, 15, 28, and 42 will be summarized by treatment group using descriptive statistics. Line plots of mean of orthostatic change in HR, SBP, and DBP measured while in supine and while in standing by treatment group will be provided.

Potentially clinically important criteria for orthostatic hypotension are defined as follows:

- $\geq 25\%$ increase in orthostatic HR

- $\geq 25\%$ decrease in orthostatic SBP
- $\geq 25\%$ decrease in orthostatic DBP
- ≥ 20 mmHg decrease in orthostatic SBP
- ≥ 10 mmHg decrease in orthostatic DBP

For each of the criteria, the frequency and proportion (expressed in percent) of participants who met the criterion at each time point will be provided by treatment group. For the by-time point summary, the denominator for the proportion is the number of participants in the treatment group with non-missing values at the given time point.

Any day that a participant met a potentially clinically important criterion of orthostatic hypotension will be counted toward the number of days with orthostatic hypotension in the study for that individual. Number of days with orthostatic hypotension will be summarized by treatment group using descriptive statistics for each of the criteria.

Additionally, categorical number of days with orthostatic hypotension will be summarized by treatment group as follows:

- 1-3 days
- 4-6 days
- 7-9 days
- 10-12 days
- 13-15 days
- ≥ 16 days

The summary will include the frequency and proportion (expressed in percent) of participants for each category. For computing proportions, the denominator will be the number of participants in the treatment group who met the respective criterion.

12.6 Electrocardiogram

12.6.1 Intraday ECG Results

Intraday values of ECG variables (HR, QRS duration, RR, PR, QT, and QTcF intervals) measured at predose, and 2.5h, 10.5h, and 16.5h after the time of 1st daily dose of study drug on Days 1, 4, 7, 10, and 14 and changes from predose taken on the same day will be summarized using descriptive statistics by treatment group.

Potentially clinically important criteria for QTcF are defined as follows:

- Observed: 451 to 480, 481 to 500, and >500 msec
- Change from predose taken on the same day: 31 to 60, and >60 msec

For each of the criteria, the frequency and proportion (expressed in percent) of participants who met the criterion at each time point will be provided by treatment group. For the by-time point summary, the denominator for the proportion is the number of participants in the treatment group with non-missing values at predose and the given post-predose time point taken on the same day.

Additionally, intraday value of ECG variables for sex subgroup (female and male) will be summarized similarly as described above. Boxplots of intraday values of QTcF by treatment group and sex will be provided.

